## 7.2 Cobimetinib plus Atezolizumab and CDX-1127 (varlilumab) (Treatment Arm A patients only)

### 7.2.1 Recommended Cobimetinib Dose Modifications

In order to standardize the management of AEs, suggested treatment management algorithms for adverse events of particular concern for cobimetinib plus atezolizumab & CDX-1127 (varlilumab) are included in Section 7.3. The following general dose modifications table for cobimetinib is for AEs not specified in the subsequent tables.

| Grade (CTCAE) a  | Recommended Cobimetinib Dose   |
|---|--|
| Grade 1 or Grade 2 (tolerable)  | No dose reduction. Maintain cobimetinib at a dose of 60 mg QD (3 tablets)            |
| Grade 2 (intolerable) or Grade 3 b or 4 (any)
First appearance | Interrupt treatment until Grade $\leq 1$ , restart treatment at 40 mg QD (2 tablets) |
| Second appearance  | Interrupt treatment until Grade $\leq 1$ , restart treatment at 20 mg QD (1 tablet)  |
| Third appearance   | Consider permanent discontinuation   |

CTCAE = Common Terminology Criteria for Adverse Events; NCI = National Cancer Institute; QD = once daily.

a The intensity of clinical adverse events graded by NCI CTCAE v5.0.

b An exception to this is for Grade 3 anemia, without presence of hemorrhage and/or hemolytic process. In this case, participants can be treated with transfusions as needed in order to improve to grade 2 or better and do not require treatment interruption or dose

reduction. If recurrent transfusions are needed, treating provider can consider dose reduction.

Toxicities will be evaluated using NCI CTCAE v5.0. If toxicity occurs, the toxicity will be graded and appropriate supportive care treatment will be administered to decrease symptoms.

Generally, in the case of Grade 4 hematologic or Grade 3 to 4 non-hematologic toxicity (except for Grade 3 skin cancer, squamous or basal cell type), treatment with cobimetinib should be interrupted until recovery to baseline or Grade 1 and then resumed at one dose level reduction. Below is a table for cobimetinib dosing upon dose modification:

| Dose level | Dose                             |
|------------|----------------------------------|
| 0          | 60 mg QD 21 days out of 28 days  |
| (-1)       | 40 mg QD, 21 days out of 28 days |
| (-2)       | 20 mg QD, 21 days out of 28 days |

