#### 7.2.2 Management of Cobimetinib plus Atezolizumab and CDX-1127 (varlilumab)–Associated Adverse Events of particular concern (Treatment Arm A)

Due to the triplet combination acting through a range of mechanisms with potential overlapping and also distinct adverse events (AE), patients who experience intolerance or adverse events should be carefully evaluated to examine whether the AE can attributable to one of the two classes of therapies: 1) targeted therapy (cobimetinib); 2) immunotherapy [Atezolizumab and CDX-1127 (varlilumab)]. For example, a patient removed from cobimetinib therapy after developing retinal vein occlusion may continue on with their Atezolizumab and CDX-1127 (varlilumab) combination. If there is ambiguity regarding the responsible drug/class of drug, all three agents should be held/discontinued with special consideration for full/partial regimen resumption as indicated by management guidelines detailed in section 7.3.

Below are recommended management of specific adverse events of particular concern with the triplet combination therapy are provided here.

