| Creatine Kinase (CPK) Elevation | General Guidance  | 
Rule out cardiac cause (check ECG, serum cardiac troponin, and CPK-isoforms M and B fraction) and rule out rhabdomyolysis (clinical examination; serum creatinine, potassium, calcium, phosphorus, uric acid, and albumin; and urine myoglobin).
 
Permanently discontinue atezolizumab & CDX-1127 (varlilumab) if there is evidence of clinically significant cardiac injury or rhabdomyolysis.. Assess patient for any history of strenuous physical activity, blunt trauma, or recent IM injections.
 | 
Rule out cardiac cause (check ECG, serum cardiac troponin, and CPK-isoforms M and B fraction) and rule out rhabdomyolysis (clinical examination; serum creatinine, potassium, calcium, phosphorus, uric acid, and albumin; and urine myoglobin).
 
Permanently discontinue atezolizumab & CDX-1127 (varlilumab) and cobimetinib if there is evidence of clinically significant cardiac injury or rhabdomyolysis.
 
Assess patient for any history of strenuous physical activity, blunt trauma, or recent IM injections.
 |
|                                 | Grade 3 that are asymptomatic and deemed not clinically significant | 
Hold atezolizumab & CDX-1127 (varlilumab) pending workup to rule out immune related cardiomyopathy, myocarditis or other cardiac conditions.
 
Workup should generally include ECG, serum cardiac troponin, and CPK-isoforms M and B fraction.
 
Atezolizumab & CDX-
   | 
Hold atezolizumab & CDX-1127 (varlilumab) and cobimetinib pending workup to rule out immune related cardiomyopathy, myocarditis or other cardiac conditions.
 
Workup should generally include ECG, serum cardiac troponin, and CPK-isoforms M and B fraction.
  |

|  |   |  |  |
|--|---|--|--|
|  |   | 
1127 (varlilumab) at fixed dosage only if cardiac etiology is ruled out.
 
Recheck CPK at least once a week. If CPK remains Grade 3 or decreases, continue Atezolizumab & CDX-1127 (varlilumab) at fixed dosage.
   | 
Atezolizumab & CDX-1127 (varlilumab) and cobimetinib may be restarted at previous dose and schedule only if cardiac etiology is ruled out.
 
Recheck CPK at least once a week. If CPK remains Grade 3 or decreases, continue Atezolizumab & CDX-1127 (varlilumab) and cobimetinib at fixed dosage and cobimetinib at current dose and schedule.
  |

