| Myositis                                      | Grade 1    | Continue atezolizumab & CDX-1127

Refer patient to rheumatologist or neurologist.

Initiate treatment as per institutional guidelines.  | Continue atezolizumab & CDX-1127 and cobimetinib

Refer patient to rheumatologist or neurologist.

Initiate treatment as per institutional guidelines.   |
|   | Grade 2    | Withhold atezolizumab & CDX-1127 (varlilumab).

Refer patient to rheumatologist or  | Withhold atezolizumab & CDX-1127 (varlilumab) and cobimetinib. a

Refer patient to  |

|         |   |  |
|---------|---|--|
|         | 
neurologist.
 
Initiate treatment as per institutional guidelines.
 
Consider treatment with corticosteroids equivalent to 1–2 mg/kg/day IV methylprednisolone and convert to 1–2 mg/kg/day oral prednisone or equivalent upon improvement.
 
If corticosteroids are initiated and event does not improve within 48 hours after initiating corticosteroids, consider adding an immunosuppressive agent.
 
If event resolves to Grade 1 or better, resume.
 
If event does not resolve to Grade 1 or better while withholding infusions, permanently discontinue infusions. c
 | 
rheumatologist or neurologist.
 
Initiate treatment as per institutional guidelines.
 
Consider treatment with corticosteroids equivalent to 1–2 mg/kg/day IV methylprednisolone and convert to 1–2 mg/kg/day oral prednisone or equivalent upon improvement.
 
If corticosteroids are initiated and event does not improve within 48 hours after initiating corticosteroids, consider adding an immunosuppressive agent.
 
If event resolves to Grade 1 or better, resume infusions at some dose and cobimetinib at 1 dose reduction.
 
If event does not resolve to Grade 1 or better while withholding study therapy, permanently discontinue therapy. c
 |
| Grade 3 | 
Withhold atezolizumab & CDX-1127 (varlilumab).
 
Refer patient to rheumatologist or neurologist.
 
Initiate treatment as per institutional guidelines.
   | 
Withhold atezolizumab & CDX-1127 (varlilumab).
 
Refer patient to rheumatologist or neurologist.
 
Initiate treatment as per institutional guidelines.
  |

|  |   |  |
|--|---|--|

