|  | 
Respiratory support may be required in more severe cases.
 
Initiate treatment with corticosteroids equivalent to 1–2 mg/kg/day IV methylprednisolone, or higher-dose bolus if patient is severely compromised (e.g., cardiac or respiratory symptoms, dysphagia, or weakness that severely limits mobility); convert to 1–2 mg/kg/day oral prednisone or equivalent upon improvement.
 
If event does not improve within 48 hours after initiating corticosteroids, consider adding an immunosuppressive agent.
 
If event resolves to Grade 1 or better, resume study therapy.
 
If event does not resolve to Grade 1 or better while withholding study therapy, permanently discontinue.
 
For recurrent events, treat as a Grade 4 event.
 | 
Respiratory support may be required in more severe cases.
 
Initiate treatment with corticosteroids equivalent to 1–2 mg/kg/day IV methylprednisolone, or higher-dose bolus if patient is severely compromised (e.g., cardiac or respiratory symptoms, dysphagia, or weakness that severely limits mobility); convert to 1–2 mg/kg/day oral prednisone or equivalent upon improvement.
 
If event does not improve within 48 hours after initiating corticosteroids, consider adding an immunosuppressive agent.
 
If event resolves to Grade 1 or better, resume infusions at some dose and cobimetinib at 1 dose reduction.
 
If event does not resolve to Grade 1 or better while withholding study treatment, permanently discontinue study treatment.
 
For recurrent events, treat as a Grade 4 event.
 |
|--|---|--|

|  |         |   |   |
|--|---------|---|---|

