|  | Grade 4 | 
Permanently discontinue atezolizumab & CDX-1127 (varlilumab). c
 
Refer patient to rheumatologist or neurologist.
 
Initiate treatment as per institutional guidelines.
 
Respiratory support may be required in more severe cases.
 
Initiate treatment with corticosteroids equivalent to 1–2 mg/kg/day IV methylprednisolone, or higher-dose bolus if patient is severely compromised (e.g., cardiac or respiratory symptoms, dysphagia, or weakness that severely limits mobility); convert to 1–2 mg/kg/day oral prednisone or equivalent upon improvement.
 
If event does not improve within 48 hours after initiating corticosteroids, consider adding an immunosuppressive agent.
 
If event resolves to Grade 1 or better, taper corticosteroids over ≥1 month.
 | 
Permanently discontinue atezolizumab & CDX-1127 (varlilumab) and cobimetinib. c
 
Refer patient to rheumatologist or neurologist.
 
Initiate treatment as per institutional guidelines.
 
Respiratory support may be required in more severe cases.
 
Initiate treatment with corticosteroids equivalent to 1–2 mg/kg/day IV methylprednisolone, or higher-dose bolus if patient is severely compromised (e.g., cardiac or respiratory symptoms, dysphagia, or weakness that severely limits mobility); convert to 1–2 mg/kg/day oral prednisone or equivalent upon improvement.
 
If event does not improve within 48 hours after initiating corticosteroids, consider adding an immunosuppressive agent.
 
If event resolves to Grade 1 or better, taper corticosteroids over ≥1 month.
 |
|--|---------|---|---|

|  |                          |  |  |
|--|--------------------------|--|--|
| Neuropathy,
immune-related
(sensory and/or
motor)                   | All Grades               | See Section 7.1.2 for
further instructions.   | See Section 7.1.2 for
further instructions.   |
|  | Grade 1                  |  |  |
|  |                          |  |  |

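### Section 7.3: the Arm A Grade 3 myositis line does not hold cobimetinib, although Grade 2 holds it, Grade 4 stops it, and the same Grade 3 cell restarts it one dose level lower

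*Combined protocol and SAP*

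**What the plan says.** Section 7.3 has one management column for the antibody doublet and one for cobimetinib plus the doublet; the second governs Arm A. For myositis, the Arm A column says:

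- Grade 1: continue all three drugs, with cobimetinib named.
- Grade 2: "Withhold atezolizumab & CDX-1127 (varlilumab) and cobimetinib".
- Grade 3: "Withhold atezolizumab & CDX-1127 (varlilumab"), a complete sentence identical to the one in the doublet column.
- Grade 4: permanently discontinue atezolizumab and "CDX-1127 (varlilumab) and cobimetinib".

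Once a Grade 3 event has resolved to Grade 1 or better, the Arm A cell directs the site to "resume infusions at some dose and cobimetinib at 1 dose reduction". If it does not resolve, the cell refers to the period during which study treatment as a whole was withheld.

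Three rules elsewhere bear on the same patient:

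- Section 7.2.1, general prose: for Grade 3 to 4 non-hematologic toxicity, "treatment with cobimetinib should be interrupted until recovery to baseline or Grade 1 and then resumed at one dose level reduction".
- Section 7.2.2: if the responsible drug is unclear, "all three agents should be held/discontinued".
- Section 7.3, Grade 3 CPK elevation, Arm A: hold the antibodies "and cobimetinib pending workup to rule out immune related cardiomyopathy, myocarditis or other cardiac conditions".

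**The concern.** The instruction does not rise with severity. Cobimetinib is stopped at Grade 2 and at Grade 4, but at Grade 3 the action line leaves it out and the same cell then restarts it at a reduced dose. A site following the action line would hold the infusions and could leave the patient taking cobimetinib.

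The protocol itself links cobimetinib to muscle injury. Section 2.2.2.2.3 describes CPK elevation and rhabdomyolysis, and the cobimetinib CAEPR lists raised CPK as likely (over 20%) and rhabdomyolysis as rare but serious. Cobimetinib is also the drug taken daily at home on Days 1 to 21, whereas the antibodies are infused every two weeks. Holding only the infusions may therefore change nothing for some days, while a cobimetinib hold acts at once. Section 2.3.4 states that this is the first human study of the triplet.

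What is at stake is patient management in Arm A, not the statistical design.

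**Working it through.** The main check is a comparison of text. There is no plan figure to reproduce.

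**Step 1. Cobimetinib in the Arm A myositis cells.**

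| Grade | Action line | Cobimetinib named? | Restart instruction for cobimetinib |
|---|---|---|---|
| 1 | Continue | Yes | Not applicable |
| 2 | Withhold | Yes | One dose reduction |
| 3 | Withhold | **No** | One dose reduction |
| 4 | Permanently discontinue | Yes | None |

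Grade 3 is the only grade whose action line omits the drug, and its restart instruction presupposes a stop that the line never orders. The sentence is complete and the rest of the cell is intact, so redaction or a page break does not explain the gap.

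**Step 2. Does another rule supply the hold?**

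- The general dose table in Section 7.2.1 "is for AEs not specified in the subsequent tables". Myositis is specified in Section 7.3, so that table does not apply.
- The prose below that table carries no such limit and does point to a hold. It is introduced as what generally applies, and it stands apart from the event-specific row.
- The Section 7.2.2 rule operates only when attribution is unclear. The same paragraph allows the two drug classes to be managed separately, and it refers resumption back to Section 7.3.
- The Grade 3 CPK row covers elevations that are asymptomatic and judged not clinically significant. The next row covers Grade 4, or any grade with signs of cardiac or renal injury. Symptomatic Grade 3 myositis with Grade 3 CPK and no such injury fits neither. The Grade 3 CPK row also lets cobimetinib restart at its previous dose, whereas the myositis cell requires a reduction.

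**Step 3. Could the omission be deliberate?** Section 7.3 does treat the classes differently elsewhere: Grade 3 hemorrhage, Grade 3 or 4 hepatic events and retinal vein occlusion. The action line alone therefore does not settle whether the difference is meant. The restart sentence does: cobimetinib was meant to be held.

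**Step 4. How many patients?** Inputs: 32 patients in Arm A (Section 9.2); myositis in the under-3% column of the atezolizumab CAEPR (Section 10.1.1.1). The lower rates are assumptions. Expected cases = n × p; chance of at least one = 1 − (1 − p)^n.

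| Assumed rate p, any grade | 32 × p | 1 − (1 − p)^32 |
|---|---|---|
| 1% | 0.32 | 0.275 |
| 2% | 0.64 | 0.476 |
| 3% (ceiling) | 0.96 | 0.623 |

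These are any-grade figures. The documents give no Grade 3 rate and no rate for the triplet.

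**Step 5. The restart wording.** Section 7.1.1 fixes the antibody doses and allows no modification, so resuming at 'some' dose has no meaning. The renal dysfunction row (Grade 3 or 4, Arm A) says 'same' in the parallel instruction.

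**The case against.** The strongest reply is that no site reads one line in isolation. Read whole, the cell has one workable meaning, because it restarts cobimetinib at a lower dose and speaks of study treatment having been withheld. The Section 7.2.1 prose supplies the matching stop, and the scope limit there applies to the table, not to the prose. Muscle injury is listed for both drug classes, so attribution will often be unclear and Section 7.2.2 would then hold everything. Where Section 7.3 splits the classes on purpose, the rows cited above state the action for each class, so silence here looks like a slip. The algorithms are described as suggested, and recurrent Grade 3 events are managed as Grade 4, where cobimetinib is named. On this view the point is editorial.

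Most of this stands as evidence of intent. It also lowers the risk: an attentive site would probably hold the drug, and only first Grade 3 episodes are exposed. It does not make the line correct. The reader must override an event-specific action with a general rule or work backward from a restart condition, at the moment a serious toxicity is being managed. Calling the algorithms suggested does not justify a Grade 3 action line that is weaker than the Grade 2 line. The 'some' for 'same' slip is purely editorial.

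**Conclusion.** The point holds. The Arm A Grade 3 myositis line is wrong as written and inconsistent with Grades 2 and 4 and with its own restart instruction. The intended action, a hold of all three drugs, can be recovered from the rest of the cell and from Section 7.2, so this is a drafting error in a safety instruction and not a gap in the safety plan.

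Its reach is small. At most about one myositis case of any grade would be expected in Arm A (0.96 at the 3% ceiling, 0.32 at an assumed 1%), and fewer at Grade 3. This assumes that the triplet's rate does not exceed the ceiling listed for atezolizumab, which the documents cannot confirm. No endpoint, error rate, power or sample size is affected. It should be corrected at the next amendment because it governs dosing during a serious event.

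**What to change.** In Section 7.3, Myositis, Grade 3, Arm A column, make the first line match the Grade 2 line: "Withhold atezolizumab & CDX-1127 (varlilumab) and cobimetinib". In the Arm A Grade 2 and Grade 3 restart sentences, change 'some' to 'same'. The doublet column is correct and stays as it is.

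The cost is two words added in one cell and one word corrected in each of two cells. Design, data collection and analysis do not change.

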|  | 
prednisone or equivalent.
 
If event does not improve within 48 hours after initiating corticosteroids, consider adding an immunosuppressive agent.
 
If event resolves to grade 1 or better, taper corticosteroids over <math>\geq 1</math> month.
 
Resumption of atezolizumab atezolizumab & CDX-1127 (varlilumab) may be considered in patients who are deriving benefit and have fully recovered from the immune-mediated event. The decision to re-challenge patients with atezolizumab should be based on investigator's assessment of benefit-risk and documented by the investigator (or an appropriate delegate). For grade 3 AEs, patient may only resume after consultation with the trial PI; for grade 4, patient cannot resume treatment, regardless of benefit.
 | 
with 1–2 mg/kg/day oral prednisone or equivalent.
 
If event does not improve within 48 hours after initiating corticosteroids, consider adding an immunosuppressive agent.
 
If event resolves to grade 1 or better, taper corticosteroids over <math>\geq 1</math> month.
 
Resumption of atezolizumab atezolizumab & CDX-1127 (varlilumab) and cobimetinib at 1 level dose reduction may be considered in patients who are deriving benefit and have fully recovered from the immune-mediated event. The decision to re-challenge patients with atezolizumab & CDX-1127 (varlilumab) and cobimetinib should be based on investigator's assessment of benefit-risk and documented by the investigator (or an appropriate delegate). For grade 3 AEs, patient may only resume after consultation with the trial PI; for grade 4, patient cannot resume treatment, regardless of benefit.
 |
|--|---|---|

|               |              |   |   |
|---------------|--------------|---|---|

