| Pancreatitis,
immune related | Grade 2 or 3 | 
Hold atezolizumab & CDX-1127 (varlilumab)
 
Refer patient to GI specialist.
 
Initiate treatment with 1–2 mg/kg/day intravenous methylprednisolone or equivalent and convert to 1–2 mg/kg/day oral prednisone or equivalent upon improvement.
 
If event resolves to grade 1 or better within 12 weeks, taper corticosteroids and resume atezolizumab & CDX-1127 (varlilumab) according to the guidelines above.
 
Permanently discontinue atezolizumab & CDX-1127 (varlilumab) if event does not resolve to grade 1 or better within 12 weeks. Patient may only resume treatment after consultation with the trial PI.
 
For recurrent events, permanently discontinue atezolizumab & CDX-1127 (varlilumab). Patient may not resume treatment, regardless of benefit.
 | 
Hold atezolizumab & CDX-1127 (varlilumab) and cobimetinib
 
Refer patient to GI specialist.
 
Initiate treatment with 1–2 mg/kg/day intravenous methylprednisolone or equivalent and convert to 1–2 mg/kg/day oral prednisone or equivalent upon improvement.
 
If event resolves to grade 1 or better within 12 weeks, taper corticosteroids and resume atezolizumab & CDX-1127 (varlilumab) and cobimetinib at same doses.
 
Permanently discontinue atezolizumab & CDX-1127 (varlilumab) and cobimetinib if event does not resolve to grade 1 or better within 12 weeks.
 
Patient may only resume treatment after consultation with the trial PI.
 
For recurrent events, permanently discontinue atezolizumab & CDX-1127 (varlilumab) and cobimetinib. Patient may not resume treatment, regardless of benefit.
 |
|---------------------------------|--------------|---|--|

|                    |                      |  |  |
|--------------------|----------------------|--|--|

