| Grade 3 or 4 | 
Permanently discontinue atezolizumab & CDX-1127 (varlilumab)
 
Bronchoscopy or BAL is recommended.
 
Initiate treatment with 1–2 mg/kg/day IV methylprednisolone or equivalent.
 
If event does not improve within 48 hours after initiating corticosteroids, consider adding an immunosuppressive agent.
 
If corticosteroids have been initiated, they must be tapered over <math>\geq 1</math> month to the equivalent
 | 
Permanently discontinue atezolizumab & CDX-1127 (varlilumab) and cobimetinib.
 
Bronchoscopy or BAL is recommended.
 
Initiate treatment with 1–2 mg/kg/day IV methylprednisolone or equivalent.
 
If event does not improve within 48 hours after initiating corticosteroids, consider adding an immunosuppressive agent.
 
If corticosteroids have been initiated, they must be tapered over <math>\geq 1</math> month to the equivalent
 |

|                   |   |   |   |
|-------------------|---|---|---|
|                   |   | 
of <math>\leq 10</math> mg/day oral prednisone before atezolizumab & CDX-1127 (varlilumab) can be resumed.
 
For grade 3 AEs, patient may only resume treatment with fixed dose atezolizumab & CDX-1127 (varlilumab) after consultation with the trial PI; for grade 4, patient cannot resume treatment, regardless of benefit.
 | 
month to the equivalent of <math>\leq 10</math> mg/day oral prednisone before atezolizumab & CDX-1127 (varlilumab) and cobimetinib can be resumed.
 
For grade 3 AEs, patient may only resume treatment with fixed dose atezolizumab & CDX-1127 (varlilumab) and 1 – level dose reduced cobimetinib after consultation with the trial PI.
 
For grade 4, patient cannot resume treatment, regardless of benefit.
 |
| Renal Dysfunction | Renal event, general guidance           | 
Consider possible tumor-related etiology, and consider earlier restaging imaging to inform clinical decision making (e.g. steroid initiation)
  | 
Consider possible tumor-related etiology, and consider earlier restaging imaging to inform clinical management (e.g. steroid initiation)
   |

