|                   | Grade 2 increased serum creatinine/CrCl | 
Withhold atezolizumab & CDX-1127 (varlilumab)
 
Refer to renal specialist for evaluation, work up and consideration of kidney biopsy to establish etiology of kidney event
 
If immune-related etiology highly suspected following work up, initiate treatment with corticosteroids equivalent to
                              | 
Withhold atezolizumab & CDX-1127 (varlilumab) & cobimetinib
 
Refer to renal specialist for evaluation, work up and consideration of kidney biopsy to establish etiology of kidney event
 
If immune-related etiology highly suspected following work up, initiate treatment with corticosteroids
  |

|  |   |   |
|--|---|---|
|  | 
1–2 mg/kg/day oral prednisone.
 
Resume in patients with complete or partial resolution (Grade 0 to 1) after appropriate intervention
 
Permanently discontinue atezolizumab & CDX-1127 (varlilumab) if no complete or partial resolution within 12 weeks of initiating steroids or inability to reduce prednisone to 10 mg per day or less (or equivalent) within 12 weeks of initiating steroids
 | 
equivalent to 1–2 mg/kg/day oral prednisone.
 
Resume in patients with complete or partial resolution (Grade 0 to 1) after appropriate intervention. Consider cobimetinib dose reduction if contributing to event
 
Permanently discontinue atezolizumab & CDX-1127 (varlilumab) & cobimetinib if no complete or partial resolution within 12 weeks of initiating steroids or inability to reduce prednisone to 10 mg per day or less (or equivalent) within 12 weeks of initiating steroids
 |
| Grade 3 or 4 increased serum creatinine/CrCl | 
Discontinue atezolizumab & CDX-1127 (varlilumab)
 
Work to evaluate etiology of renal event.
 
Refer to renal specialist for evaluation, work up and consideration kidney biopsy to establish etiology of kidney event
 
If immune-related etiology highly suspected following work up, initiate treatment with corticosteroids equivalent to
   | 
Discontinue atezolizumab & CDX-1127 (varlilumab) & cobimetinib
 
Refer to renal specialist for evaluation, work up and consideration kidney biopsy to establish etiology of kidney event
 
If immune-related etiology highly suspected following work up, initiate treatment with corticosteroids equivalent to 1–2 mg/kg/day oral prednisone.
   |

|  |  |   |   |
|--|--|---|---|

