|  |  | 
1–2 mg/kg/day oral prednisone.
 
Resume in patients with complete or partial resolution (Grade 0 to 1) after corticosteroid taper at same doses.
 
Permanently discontinue atezolizumab & CDX-1127 (varlilumab) if no complete or partial resolution within 12 weeks of initiating steroids or inability to reduce prednisone to 10 mg per day or less (or equivalent) within 12 weeks of initiating steroids
 
If event resolves to grade 1 or better, taper corticosteroids over <math>\geq 1</math> month. For grade 3 AEs, patient may only resume treatment after consultation with the trial PI; for grade 4, patient cannot resume treatment, regardless of benefit.
 | 
Resume in patients with complete or partial resolution (Grade 0 to 1) after corticosteroid taper at same doses.
 
Permanently discontinue atezolizumab & CDX-1127 (varlilumab) & cobimetinib if no complete or partial resolution within 12 weeks of initiating steroids or inability to reduce prednisone to 10 mg per day or less (or equivalent) within 12 weeks of initiating steroids
 
If event resolves to grade 1 or better, taper corticosteroids over <math>\geq 1</math> month. For grade 3 AEs, patient may only resume treatment (infusions at same dose, and cobimetinib at one dose reduction) after consultation with the trial PI; for grade 4, patient cannot resume treatment, regardless of benefit.
 |
|--|--|---|---|

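### The Arm A cell of the Grade 3 or 4 renal row in Section 7.3 gives two different cobimetinib restart doses after a Grade 3 event

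*Combined protocol and SAP*

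**What the plan says.** The row is labelled "Grade 3 or 4 increased serum creatinine/CrCl" and has one cell for the doublet and one for the Arm A triplet. Both cells have the same structure.

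- They open by discontinuing every agent in the column. In Arm A that means all three drugs.
- They then say "Resume in patients with complete or partial resolution (Grade 0 to 1) after corticosteroid taper at same doses". The sentence names no drug, sets no grade limit and does not mention the PI.
- They require permanent discontinuation if there is no resolution within 12 weeks of starting steroids, or for "inability to reduce prednisone to 10 mg per day or less (or equivalent) within 12 weeks of initiating steroids".
- They close with a steroid taper over at least a month and grade-specific restart rules. After Grade 3 the patient may resume only after consulting the trial PI. In the Arm A cell the permitted regimen is given in parentheses: "infusions at same dose, and cobimetinib at one dose reduction". In both cells, "for grade 4, patient cannot resume treatment, regardless of benefit".

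Section 7.2.1 sets the cobimetinib levels at 60, 40 and 20 mg on 21 of 28 days, with at most two reductions. Section 7.1.1 fixes the doses of both antibodies.

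**The concern.** Within one Arm A cell, a patient who recovers from a Grade 3 renal event is first told to restart at unchanged doses and then told to restart with cobimetinib one level lower. The protocol states no order of precedence between the two. When the responsible drug is unclear, Section 7.2.2 sends the site to Section 7.3 for the restart decision, so this cell is where the site would look.

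What is at stake is a restart dose after severe organ toxicity in a combination that Section 2.3.4 describes as first in human. A site that acts on the first sentence gives the higher dose and departs from the second.

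**Working it through.** No figure in the statistical plan depends on this, so the check is a comparison of texts, followed by simple dose and exposure arithmetic.

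**1. Does the first sentence cover cobimetinib?** The Arm A cell has just discontinued all three agents, so an instruction to resume naturally covers all three. Elsewhere in the table the same dosing phrase expressly includes cobimetinib: the Grade 2 or 3 pancreatitis row resumes "CDX-1127 (varlilumab) and cobimetinib at same doses", and the adrenal insufficiency and hypophysitis row does likewise. Where the authors meant the antibodies alone, they said so, as in the closing paragraph of this cell.

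**2. Which instruction is intended after Grade 3?**

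| Place | Cobimetinib on restart after Grade 3 |
|---|---|
| Renal row, first sentence | unchanged |
| Renal row, closing paragraph (Arm A) | one level lower, after PI consultation |
| Hepatic Grade 3 or 4 row (Arm A) | "cobimetinib at 1 level dose reduction may be considered" |
| Pulmonary Grade 3 or 4 row (Arm A) | "level dose reduced cobimetinib after consultation with the trial PI" |
| Section 7.2.1, general text on Grade 3 to 4 non-hematologic toxicity | one level lower |

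The Grade 2 renal row already asks the site to consider a cobimetinib reduction if the drug contributed. An unreduced restart after Grade 3 would be less cautious than the Grade 2 rule. The first sentence is the outlier.

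**3. Is there a dose conflict in the doublet column?** No. Both antibodies are fixed-dose, so restarting them at the same dose is the only option.

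**4. Size of the dose difference** (daily dose × 21 days per cycle):

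- Level 0: 60 × 21 = 1260 mg. Level −1: 40 × 21 = 840 mg. Level −2: 20 × 21 = 420 mg.
- From the starting dose the two instructions differ by 1260 − 840 = 420 mg per cycle.
- From level −1 they differ by 840 − 420 = 420 mg per cycle.
- At 20 mg no lower level exists. The first sentence restarts 20 mg, and the closing rule cannot be carried out as written.

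**5. Patients exposed.** The protocol gives no renal event rate for this triplet. As an assumption, take the atezolizumab adverse event list in Section 10.1.1.1, which puts creatinine increase, acute kidney injury and nephritis each in the category under 3%. Section 9.2 plans 32 patients per arm.

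- Arm A: 0.03 × 32 = 0.96, so fewer than about one patient per term. The range runs from 0 up to that figure.
- This counts any grade. The dose conflict also needs a Grade 3 event, recovery to Grade 0 or 1 and a decision to restart, so the expected number is lower still.

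**The case against.** The strongest reply is that the cell resolves itself. The closing paragraph is later and grade-specific, and its wording is exclusive: after Grade 3 a patient may resume only on the stated terms. The first sentence names no drug and is identical to the doublet sentence, so it could be read as applying to the infusions alone. Every Grade 3 restart passes through the trial PI, and Section 7.2.1 calls the Section 7.3 algorithms suggested. Much of this stands. A careful reader would probably follow the closing paragraph, and consultation lowers the risk. It does not remove the contradiction, because the first sentence carries no cross-reference to the later rule and consultation does not settle which dose the cell prescribes.

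A reader might infer three stronger things that the documents do not support.

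- **That the protocol permits restart after Grade 4.** Taken alone, the first sentence has no grade limit. But the same cell, in both columns, expressly forbids a Grade 4 restart, so this is a general permission followed by a specific ban. Section 9.5.1 points the same way by implication: its run-in list counts Grade 4 events as unacceptable toxicity, and creatinine is not among the named exceptions.
- **That the 3.6% rate in Section 2.2.2.2.3 measures exposure.** That figure is a large CPK rise with a concurrent creatinine rise on cobimetinib plus vemurafenib. Here the CPK row sends CPK elevation with renal injury to permanent discontinuation of all three agents, so such patients would not normally reach the renal restart sentence.
- **That the first sentence is the only taper safeguard for cobimetinib.** The general taper guidance in Section 7.1.2 does name only the antibodies. But the renal cell's closing paragraph has its own taper of at least a month, and its 12-week rule stops cobimetinib if prednisone cannot be brought down to 10 mg daily.

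**Conclusion.** The point holds for the Arm A cell after Grade 3: two incompatible cobimetinib doses are prescribed for the same patient, one level apart (60 or 40 mg daily, or 40 or 20 mg). The reduction is evidently intended. The missing grade limit in both columns deserves tidying, but it does not open a Grade 4 restart.

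The expected number affected is below about 1 of 32 Arm A patients per renal term at any grade. This assumes that the atezolizumab category of under 3% carries over to the triplet, which the protocol does not establish. Sample size, power, type I error and every efficacy analysis are unaffected.

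This is a minor but real safety correction. The exclusive wording of the closing rule and the PI consultation keep it from being a serious defect.

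**What to change.** Replace the first sentence in both columns with:

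> Grade 3 only: after consultation with the trial PI, once resolved to Grade 0–1 and, if corticosteroids were started, after taper to prednisone 10 mg/day or less, resume infusions at the same dose [Arm A column: and cobimetinib one dose level lower; if already at 20 mg, discontinue cobimetinib]. Grade 4: permanently discontinue.

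Keep the 12-week discontinuation rule. The wording otherwise restates the cell's own closing rule. The one addition is the 20 mg case, which follows the Section 7.2.1 text that stops cobimetinib for recurrent toxicity after two reductions. The general table there says only to consider stopping, so the sponsor should confirm that clause.

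The cost is one sentence in each of two table cells at the next amendment, with no change to design, sample size or analysis.
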